8.2. Treatment Compliance

8.2.1. Dose Delays

Dose delay is the difference between the actual time between two consecutive non-zero doses and the planned time between the same two consecutive non-zero doses.

Dose delay for dose x (days) = Date of dose x – Date of dose (x-1) – Planned days between two consecutive doses.

Dose delays will be grouped into the following categories:

- No delay
 - 0 days delay
 - o 1-3 days delay
- 4-6 days delay
- 7 or more days delay

For example, for PF-07901801, initially administered on a weekly schedule, if one participant receives PF-07901801 on Day 1, then the next PF-07901801 administration date will be on Day 8; however, if the participant receives PF-07901801 at Day 9 or 10, this is considered as 1-3 days delay.

The number and percentage of participants with delayed study drug administration and maximum length of delay, *i.e.*, the worst case of delay if participants have multiple dose delays will be summarized for the overall study.

8.2.2. Dose Reductions

Dose reduction is defined as actual non-zero dose < 90% of the planned dose. The number and percentage of participants with at least one dose reduction as well as a breakdown of the number of dose reductions (1, 2, 3, \ge 4) will be summarized.

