5.3 Criteria for Treatment Discontinuation

Participants may withdraw voluntarily from participation in the study or from study treatment at any time and for any reason. A participant 's participation in the study may terminate at his/her/their request or on the basis of the investigator's clinical judgment. The reason for participant withdrawal will be documented in the source data and noted on the electronic case report form (eCRF).

At a minimum, all participants who discontinue study treatment, including those who refuse to return for a final visit, will be contacted for safety evaluations at the 30-Day Safety Follow-Up Visit.

If such withdrawal occurs, or if the participant fails to return for visits, the investigator must determine the primary reason for a participant's withdrawal from the study and record the information on the eCRF. If the reason for withdrawal is an adverse event, monitoring should continue until the outcome is evident. The specific event or test result(s) must be recorded in the eCRF. At the discretion of the sponsor, participants may also be removed from the study.

It should be clearly documented in the source data whether participants withdrew consent for participation in the study, including study treatment and participation in the long-term follow-up phase or if participants withdrew from study treatment but will continue further participation in the long-term follow-up portion of the study.

Treatment may be continued until one of the following criteria applies:

- An unacceptable adverse event or safety observation, such as a persistent moderate toxicity that is intolerable to the participant, that is in the opinion of the investigator clearly attributed to PF-07901801.
- An unacceptable adverse event or safety observation, such as a persistent moderate toxicity that is intolerable to the participant, that is in the opinion of the investigator clearly attributed to PLD and the participant has received fewer than four cycles of PLD. A participant who has completed four cycles of PLD treatment and experiences an adverse event that requires discontinuation of PLD may continue on study receiving PF-07901801 monotherapy after discussion with the sponsor medical monitor.
- Any event which would cause PF-07901801 or PLD to be modified by more than two
 dose reductions or to be held for more than 42 days from the last administered dose and
 is not attributable to a particular agent of the combination regimen; exception is made

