9.1.3 PF-07901801 Dose Modification Guidelines

Table 15 describes modifications for the dose levels intended to be evaluated in the dose escalation portion of the study.

Table 15. PF-07901801 Dose Modifications

Dose Level	Dose Level -1	Dose Level -2
48 mg/kg	32 mg/kg	24 mg/kg
24 mg/kg	18 mg/kg	12 mg/kg
12 mg/kg	8.0 mg/kg	4.0 mg/kg

While PF-07901801 has demonstrated clinical activity in Study TTI-622-01 at dose levels as low as 0.8 mg/kg, the agent has demonstrated a very promising safety profile suggesting that dose reductions may not be routinely required. Thus, the study does not prospectively envision

requirement for a dose level below 4.0 mg/kg but a lower dose level may be allowed after consultation with the sponsor medical monitor for a participant who is receiving disease control and remaining on treatment is, in the opinion of the investigator, a reasonable treatment option for the participant.

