A participant who completes at least four cycles of treatment with PF-07901801 in combination with PLD and requires discontinuation of PLD due to PLD-related toxicity and who is receiving disease control may continue on study receiving PF-07901801 monotherapy beginning with the next cycle provided the participant has not experienced disease progression and PF-07901801 re-treatment guidelines as described in Section 9.1.2 of the protocol are met.

Exposure to PF-07901801 and PLD will be summarized with descriptive statistics for the number of non-zero doses received, duration of dosing (weeks), total cumulative dose (mg/kg for PF-07901801, mg/m² for PLD), and overall relative intensity.

Duration of treatment is defined as the time (in weeks) from first dose of study drug in cycle 1 to the last dose of study drug in the last cycle a participant had.

Total cumulative dose is the sum of the actual doses of PF-07901801 or PLD received.

Pfizer Inc. / Protocol: C4971002 (TTI-622-02) IQVIA Biotech (Confidential) Project # ZZA82397

The calculation algorithm for duration of exposure (in weeks) for each drug and intended duration of PF-07901801 treatment will be:

- Duration of PLD exposure (weeks) = (Last PLD dose date first PLD dose date + 28) / 7
- Duration of PF-07901801 exposure (weeks)
 - DL1 and DL2 → If the last dose occurs during cycle 1: (Last PF-07901801 dose date first PF-07901801 dose date + 7) / 7
 - DL1 and DL2 → If the last dose occurs during cycle 2 and beyond: (Last PF-07901801 dose date – first PF-07901801 dose date + 14) / 7
 - DL3: (Last PF-07901801 dose date first PF-07901801 dose date + 14) / 7

Overall relative intensity (in %) for each drug is calculated as 100 × cumulative dose received divided by cumulative dose planned, where:

- Cumulative dose of PLD planned (mg/m²) = Planned PLD dose/cycle (40) × Duration of PLD exposure (weeks)
- Cumulative dose of PLD received (mg/m²) = Sum of all PLD doses (mg/m²) actually received.
- Relative Dose Intensity (%) of PLD = Cumulative dose of PLD planned (mg/m²) / Cumulative dose
 of PLD received (mg/m²) × 100%
- Cumulative dose of PF-07901801 planned (mg/kg), where D = planned dose for the participants according to the DL (12, 24 or 48 mg/kg) and C = number of treatment cycles:

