 - DL1 and DL2: (planned PF-07901801 dose/cycle × cycle 1 × number of planned administrations of PF-07901801 in cycle 1) + (planned PF-07901801 dose/cycle × number of cycles of PF-07901801 after cycle 1 × number of planned administrations of PF-07901801 per cycle) = (D × 1 × 4) + (D × [C-1] × 2)
 - DL3: planned dose/cycle × number of cycles of PF-07901801 × number of planned administrations of PF-07901801 per cycle = 48 × C × 2
- Cumulative dose of PF-07901801 received (mg/kg) = Sum of all PF-07901801 doses (mg/kg) actually received.
- Relative Dose Intensity (%) of PF-07901801 = Cumulative dose of PF-07901801 planned (mg/m²)
 / Cumulative dose of PLD received (mg/m²) × 100%

The number of drug administrations with dose reduction, infusion held or permanently withdrawn will also be

Pfizer Inc. / Protocol: C4971002 (TTI-622-02) IQVIA Biotech (Confidential) Project # ZZA82397

summarized descriptively by cohort, for each study drug (PF-07901801 and PLD).

In addition, the planned dosing date and the actual dosing date will be listed. Listings will be provided with the information from all the study drug administration eCRFs. Reasons for missed doses of PF-07901801 and PLD will be listed.

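### SAP 8.2.2, read with the planned dose used in SAP 8.1, counts one lasting dose reduction again at every later infusion, so its 1/2/3/≥4 breakdown does not give the protocol's number of reductions

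*SAP*

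**What the plan says.** SAP 8.2.2 gives the rule: "Dose reduction is defined as actual non-zero dose < 90% of the planned dose". It reports the number and percentage of participants with at least one reduction, "as well as a breakdown of the number of dose reductions" in the categories 1, 2, 3 and ≥4. It does not define planned dose, and it has no rule for a reduction that persists.

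SAP 8.1 is the only place where the SAP puts a value on the planned dose. For PF-07901801 it writes "where D = planned dose for the participants according to the DL (12, 24 or 48 mg/kg"). For PLD it enters a fixed 40 mg/m² per cycle. Neither value changes after a dose modification. The same section separately announces a per-administration summary by cohort and drug: "The number of drug administrations with dose reduction, infusion held or permanently withdrawn will also be" summarised.

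The protocol uses the term for a step to a lower level. Section 9.1.3 introduces the PF-07901801 steps: "Table 15 describes modifications for the dose levels intended to be evaluated in the dose escalation portion of the study". That table gives two lower levels for each starting dose. Table 22 gives a first and a second reduction for PLD. Among the criteria for stopping treatment, Section 5.3 lists an event that would cause "PF-07901801 or PLD to be modified by more than two" dose reductions, subject to conditions and exceptions. Section 9.2 says that a PLD dose reduced for toxicity should in general not be raised again.

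**The concern.** The SAP and the protocol use the same term for different things. In the protocol, one reduction is one change of level, however long the participant stays on the lower level. The SAP test is applied to each administered dose, so a participant kept on one lower level keeps adding to the count.

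Tolerability of the escalating doses is part of the Phase 1 primary objective, and these exposure tables describe it by cohort. Under the SAP rule, a participant who does well on a single PF-07901801 step for three cycles (6 flagged infusions, category ≥4) looks less tolerant than one who needed two steps and stopped after one infusion at each (category 2). The rule also flags an infusion that was stopped early. Protocol Table 20 has a PF-07901801 infusion stopped if symptoms return after a Grade 3 infusion reaction, and says that the dose need not be reduced. If less than 90% was delivered, the SAP would still record a reduction.

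**Working it through.** The plan states no figure on this point, so there is none to reproduce. The check counts flagged infusions.

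**Inputs**
- Flag (SAP 8.2.2): 0 < actual dose < 0.9 × planned dose.
- Planned dose (SAP 8.1): 12, 24 or 48 mg/kg; PLD 40 mg/m².
- Steps: protocol Table 15 (PF-07901801) and Table 22 (PLD).
- Infusions per cycle from Cycle 2 (protocol 5.2): two of PF-07901801, one of PLD.

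**Step 1. Does each step fall below the threshold?**

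| Cohort dose | 90% threshold | First step | Second step |
|---|---|---|---|
| 48 mg/kg | 43.2 | 32 (66.7%) | 24 (50.0%) |
| 24 mg/kg | 21.6 | 18 (75.0%) | 12 (50.0%) |
| 12 mg/kg | 10.8 | 8 (66.7%) | 4 (33.3%) |
| PLD 40 mg/m² | 36 | 30 (75.0%) | 22.5 (56.25%) |

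All do, so every infusion at a reduced level is flagged.

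**Step 2. Count for one step kept from Day 1 of cycle s to the end of cycle e.** PF-07901801: 2 × (e − s + 1). PLD: e − s + 1.

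| Step at | Treated through | PF-07901801 | PLD | Protocol count |
|---|---|---|---|---|
| Cycle 2 | Cycle 4 | 2 × 3 = 6 | 3 | 1 |
| Cycle 2 | Cycle 6 | 2 × 5 = 10 | 5 | 1 |
| Cycle 3 | Cycle 6 | 2 × 4 = 8 | 4 | 1 |

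One, two or three infusions after the step give categories 1, 2 and 3. Category ≥4 needs four such infusions: 4/2 = 2 cycles of PF-07901801 or 4/1 = 4 cycles of PLD. Two steps, 48 to 32 to 24 mg/kg with four infusions at each level, give 4 + 4 = 8 against a protocol count of 2.

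**Step 3. Other readings of planned dose**, for one step from 24 to 18 mg/kg followed by eight infusions:
- cohort dose, as in SAP 8.1: 8;
- dose prescribed after the modification: 0, because actual equals planned;
- level in force just before the infusion: 1, which is the protocol's count.

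**The case against.** The strongest defence is that per-infusion counting is deliberate. Section 8.2.2 sits under treatment compliance, a 90% threshold is a test of delivered dose, and 8.2.3 uses the same four categories for infusion interruptions, which are per-infusion events. The administration count in 8.1 is a cohort summary, whereas 8.2.2 distributes participants, so the two need not duplicate each other. This may be what was intended. But the result would still carry the protocol's term while counting something else, and no output described in the SAP would tabulate participants by number of level steps.

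Four stronger inferences are tempting, and the documents do not support them.
- *Each reduced participant lands in ≥4 or is never counted.* With one to three later infusions the category is 1 to 3, and with exactly one the count is right. The zero count needs the modified-dose reading, which has little support because 8.1 uses the cohort dose.
- *No reading can give the protocol's count.* Taking planned dose as the level in force before the infusion would, but the SAP does not say so and 8.1 points elsewhere.
- *A ≥4 entry shows a breach of a two-reduction limit.* There is no absolute cap. The Section 5.3 criterion concerns events not attributable to one agent and has a disease-control exception; Section 9.2.3 calls for consultation when more than two PLD reductions are needed; Section 9.1.3 may allow PF-07901801 levels below its table.
- *Dose selection is compromised.* Escalation rests on DLTs, safety review and PK, not on this table. The secondary safety endpoint names delays and discontinuations, not reductions.

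Other planned outputs also limit misreading: adverse events leading to dose reduction, by drug, and the dosing listings.

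**Conclusion.** The point holds for the breakdown by number of reductions. With planned dose as in SAP 8.1, one lasting step is counted once per later infusion. In the examples above, single steps appear as 3 to 10 reductions where the protocol counts one. The breakdown then reflects how long a participant stayed on treatment after a reduction.

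The examples assume that the step is kept and that treatment continues to Cycle 4 or 6. For PLD, persistence is the protocol's general rule, although an increase may be discussed with the medical monitor. For PF-07901801 it is an assumption. Shorter treatment gives smaller discrepancies.

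The effect is confined to descriptive exposure reporting. The percentage of participants with at least one reduction captures every level step, with some addition from infusions cut short below 90%. The primary DLT endpoint and the escalation rules do not depend on it. It should still be corrected: the written rule gives a wrong count of a quantity the protocol defines, and correction is cheap.

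**What to change.** In SAP 8.2.2, count a dose reduction each time the prescribed dose (mg/kg or mg/m²) is lower than the one prescribed at the previous administration. Include PLD adjustments that the protocol specifies outside Table 22, such as the bilirubin-based ones in Section 9.2.3. Tabulate participants by that count. Report infusions delivering less than 90% of the prescribed dose on a separate line, as incomplete infusions.

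Derive the count from the study drug administration eCRFs named in SAP 8.1 and from the dose-reduced category that protocol 13.5 records for each drug when action is taken for an adverse event. The documents do not list the eCRF fields, so confirm that the prescribed dose can be recovered separately from the delivered dose.

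The cost is SAP wording and one extra derived variable. SAP 1.1 allows the plan to be modified before the clinical database lock.

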8.2.3. Infusion Interruptions

An infusion interruption is defined as an infusion that is stopped and re-started on the same day (i.e., for a visit more than one infusion start time and infusion end time are recorded).

The number and percentage of participants with at least one infusion interruption as well as the frequency of participants with 1, 2, 3, or \geq 4 infusion interruptions will be summarized.

Template No.: NVA_TP_CR694 Revision 4 Reference: SOPCR008, WPCR013 Template Effective Date:15Feb2023 Page 28 of 46

Pfizer Inc. / Protocol: C4971002 (TTI-622-02) IQVIA Biotech (Confidential) Project # ZZA82397

The causality of AE is reported as either related to study drug or not related to study drug for each study drug (PF-07901801 and PLD). If the relationship to a treatment is missing, it will be considered as "related".

If a participant has multiple occurrences of an adverse event, the strongest level of relationship to study drug and the worst toxicity grade a participant experiences for a given AE will be used in these tables. No imputation will be performed for missing toxicity grade.

Template No.: NVA_TP_CR694 Revision 4 Reference: SOPCR008, WPCR013 Template Effective Date:15Feb2023 Page 29 of 46

Pfizer Inc. / Protocol: C4971002 (TTI-622-02) IQVIA Biotech (Confidential) Project # ZZA82397

AEs that have missing onset dates will be considered as TEAE unless the stop date is known to be prior to the first administration of the study medication. If the AE onset date is partial, the date will be correlated as far as possible with the date of first dose of study medication. AE will be assumed to be TEAE, unless there is clear evidence (through comparison of partial dates) to suggest that the adverse event started prior to the first dose of study medication. Detailed date imputation rules can be found in section 5.4.1. If participants died during the study and experienced AEs at the time of death, the AEs that lead to death will use death date as the AE end date; otherwise, AEs that do not lead to death will be reported as ongoing.

There are no Adverse Events of Special Interest (AESI) related to the study drugs in this protocol.

The following TEAE summary tables will be produced by dose cohort, and overall:

- An overall summary of safety will summarize the numbers (and percentages) of participants with the following:
 - TEAEs
 - Grade ≥ 3 TEAEs
 - Related TEAEs [related to PF-07901801 only, PLD only, any study drug, and both drugs]
 - Related grade ≥ 3 TEAEs [related to PF-07901801 only, PLD only, any study drug, and both drugs]
 - Serious TEAEs
 - Related Serious TEAEs [related to PF-07901801 only, PLD only, any study drug, and both drugs]
 - TEAEs leading to dose reduction (of PF-07901801 and PLD, separately)
 - TEAEs leading to drug interruption (of PF-07901801 and PLD, separately)
 - TEAEs leading to permanently discontinued study drug (PF-07901801, PLD, any drug, and both)
 - Related TEAEs [related to PF-07901801 only] leading to permanent discontinuation of PF-07901801
 - Related TEAEs (related to PLD only) leading to permanent discontinuation of PLD
 - Related TEAEs (related to both drugs) leading to permanent discontinuation of both drugs
 - TEAEs leading to death
 - Related TEAEs [related to PF-07901801 only, PLD only, any study drug, and both drugs] leading to death
- Separate summaries of TEAEs by SOC and PT, as follows:
 - All TEAEs (any grade)
 - All grade ≥ 3 TEAEs
 - Related TEAEs [related to PF-07901801 only, PLD only, any study drug, and both drugs]
 (any grade)

Pfizer Inc. / Protocol: C4971002 (TTI-622-02) IQVIA Biotech (Confidential) Project # ZZA82397

- Related TEAEs [related to PF-07901801 only, PLD only, any study drug, and both drugs] $(grade \ge 3)$
- All Serious TEAEs
- Related Serious TEAEs [related to PF-07901801 only, PLD only, any study drug, and both drugs]
- All TEAEs leading to dose reduction (of PF-07901801 and PLD, separately)
- All TEAEs leading to drug interruption (of PF-07901801 and PLD, separately)
- Related TEAEs [related to PF-07901801 only] leading to permanent discontinuation of PF-07901801
- Related TEAEs (related to PLD only) leading to permanent discontinuation of PLD
- Related TEAEs (related to both drugs) leading to permanent discontinuation of both drugs
- All TEAEs leading to death
- All related TEAEs [related to PF-07901801 only, PLD only, any study drug, and both drugs] leading to death
- Summary of infusion related reactions (any grade and Grade \geq 3) by PT
- All TEAEs by SOC, PT, and maximum severity (CTCAE toxicity grade)
- DLTs by SOC, PT, and maximum severity (CTCAE toxicity grade)

The following AE listings will be produced, sorted by dose cohort, participant, and timing, with relevant information:

- All AEs
- All DLTs
- AEs leading to death

8.5.Deaths

The frequency (number and percentage) of subjects in the SAS who died and who died within 30 days after last dose of study treatment as well as the reason for death, will be tabulated:

- All deaths
- Deaths within 30 days after last dose of study treatment
- Cause of death

In addition, date and cause of death will be provided in individual participant data listing together with selected dosing information (study treatment received, date of first / last administration, dose) and will include the following information:

CONFIDENTIAL

- AEs with fatal outcome (Listing of PTs of AEs with outcome=Fatal, as well as AEs of Grade 5)
- Flag for death within 30 days of last dose of study treatment.

Pfizer Inc. / Protocol: C4971002 (TTI-622-02) IQVIA Biotech (Confidential) Project # ZZA82397

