13.3 Assessment of Causality

The relationship of each adverse event to administration of the study drug(s) will be assessed by the investigator after careful consideration of all relevant factors such as (but not limited to) the underlying study indication, co-existing disease, concomitant medication, relevant history, pattern of the adverse event, temporal relationship to receipt of the study medication(s) and dechallenge or re-challenge.

Study drug or study treatment refers to intravenously-administered PLD and intravenously-administered PF-07901801. The assessment of relationship to study drug or study treatment will be done for each drug separately. If the investigator feels such a distinction cannot be made, the assessment will be based on the combination of the two drugs.

The assessment of causality is based on the question of whether there was a reasonable causal relationship to the study drug in question according to the following guidelines:

RELATED: there is a reasonable possibility that the study treatment caused the event; one or more of the following criteria apply:

- The event follows a reasonable temporal sequence from administration of study treatment
- The event could not be reasonably attributed to the known characteristics of the participant's clinical state, environment or toxic factors or other modes of therapy administered to the participant
- The event follows a known pattern of response to study treatment
- The event disappears or decreases on cessation or reduction in dose of the study treatment. In some situations, an adverse event will not disappear or decrease in intensity upon discontinuation of the study treatment despite other clear indications of relatedness

UNRELATED: there is no reasonable possibility that the study treatment caused the event; one or more of the following criteria apply:

- The event does not follow a reasonable temporal sequence from administration of study treatment
- The event could be reasonably attributed to known characteristics of the participant's clinical state, concurrent illness, environment or toxic factor or other therapies administered to the participant
- The event does not follow a known pattern of response to study treatment
- The event does not disappear or decrease on cessation or reduction in dose of the study treatment, and it does not reappear or worsen when the study treatment is re-administered
- There is a clear alternative explanation

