34	Incidence of Treatment Emergent Adverse Events Leading to Permanent Discontinuation of PLD and PF-07901801 by System Organ Class and Preferred Term, Number (%) of Participants	SAS
35	Incidence of Treatment-related (related to PF-07901801 only) Treatment Emergent Adverse Events Leading to PF-07901801 Permanent Discontinuation by System Organ Class and Preferred Term, Number (%) of Participants	SAS
36	Incidence of Treatment-related (related to PLD only) Treatment Emergent Adverse Events Leading to PLD Permanent Discontinuation by System Organ Class and Preferred Term, Number (%) of Participants	SAS

Pfizer Inc. / Protocol: C4971002 (TTI-622-02) IQVIA Biotech (Confidential) Project # ZZA82397

Incidence of Treatment Frelated (to both drugs) Treatment Emergent Adverse Events Leading to Permanent Discontinuation of Both PLD and PF-07901801 by System Organ Class and Preferred Term, Number (%) of Participants SAS			
Term, Number (%) of Participants SAS	37		SAS
Number (%) of Participants SAS	38		SAS

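### No related-discontinuation table counts an event related to both drugs that stops PLD alone

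*SAP*

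**What the plan says.** SAP Section 8.4 lists three related-discontinuation rows, once in the overall safety summary and again among the SOC/PT summaries:

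- The row for the investigational drug reads "Related TEAEs [related to PF-07901801 only] leading to permanent discontinuation of PF-07901801".
- The row for PLD is built the same way and takes only events attributed to PLD alone.
- The row for the combination reads "Related TEAEs (related to both drugs) leading to permanent discontinuation of both drugs".

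Appendix 1 repeats the limits in the table titles. Table 35 is "Incidence of Treatment-related (related to PF-07901801 only) Treatment Emergent Adverse Events Leading to PF-07901801 Permanent Discontinuation by System Organ Class and Preferred Term", Table 36 is the PLD counterpart with the same 'only' restriction, and Table 37 requires relation to both drugs and discontinuation of both.

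The other related-event summaries in Section 8.4 are split differently: "Related TEAEs [related to PF-07901801 only, PLD only, any study drug, and both drugs". The same four categories are applied there to related grade ≥3, serious and fatal TEAEs. Discontinuation regardless of causality also has an any-drug category, and Tables 31–34 present it by SOC and PT without relatedness.

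On data collection, Protocol Section 13.3 assesses causality for each drug separately and adds: "If the investigator feels such a distinction cannot be made, the assessment will be based on the combination of the two drugs". Protocol Section 13.5 records the action taken separately for each drug. SAP Section 8.4 counts a missing relationship as related. Protocol Sections 5.2, 5.2.2 and 5.3, and SAP Section 8.1, allow a participant who has had at least four cycles of the combination and must stop PLD for toxicity to continue on PF-07901801 alone.

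**The concern.** Tables 35–37 look like a complete split of related discontinuations, and a reader of the study report would take them that way. They match the relatedness category to the drug stopped only where the two coincide. An event judged related to both drugs that leads to stopping PLD alone is excluded from Tables 35 and 36 by the word 'only' and from Table 37 by the requirement that both drugs stop.

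Causal relationship and treatment discontinuations are both components of the overall safety profile, a secondary endpoint (Protocol Section 4.4, SAP Section 3.2). Dropping the chemotherapy partner for toxicity shared with the investigational drug bears directly on the tolerability of the combination. The missing-equals-related rule is meant to be conservative but works the other way here: a PLD-related event with missing PF-07901801 causality becomes related to both, and leaves Table 36 if only PLD is stopped.

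**Working it through.** The SAP gives no figure to reproduce; the question is which events each table can hold.

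**Step 1. Cross relatedness with the drug permanently stopped.** Each has three levels (PF-07901801 only, PLD only, both), giving 3 × 3 = 9 cells. Entries are the table that counts the cell.

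| TEAE related to | Only PF-07901801 stopped | Only PLD stopped | Both stopped |
|---|---|---|---|
| PF-07901801 only | 35 | none | 35* |
| PLD only | none | 36 | 36* |
| Both drugs | none | none | 37 |

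*Counted if discontinuation of a drug includes cases where the other drug stops too; not counted if it means that drug alone.

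Coverage is 5 of 9 cells on the inclusive reading and 3 of 9 on the strict reading. On either reading the two cells 'related to both, one drug stopped' are in no related table.

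**Step 2. Which uncovered cells can be expected to occur?**

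- *Related to both, only PLD stopped.* Plausible. Causality and action are recorded per drug, so the combination of answers can be entered, and the monotherapy provision gives the route. Section 5.2 words the trigger as PLD-related toxicity, which does not exclude a relation to PF-07901801 as well. The toxicities overlap: in the earlier PF-07901801 study, related thrombocytopenia was reported in 9 participants (21%) and related neutropenia in 5 (12%) (Protocol Table 3), and Protocol Table 24 manages the same two events as PLD-associated.
- *Related to both, only PF-07901801 stopped.* Not an expected path. The synopsis makes an unacceptable event clearly attributed to PF-07901801 a reason to withdraw from all study treatment.
- *Related to one drug only, the other drug alone stopped.* The documents describe no such route.

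**Step 3. Direction and size.** Let k be the participants whose only related discontinuation is in the 'both, PLD stopped' cell. Tables 35–37 together miss k of N. With N = 25, each such participant is 1/25 = 4 percentage points. The documents give no value for k. If k = 0 there is no shortfall.

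**Step 4. What still captures the event.** It appears in Table 31 (any drug stopped) and Table 33 (PLD stopped), without relatedness, and in Listing 15 (all AEs).

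**Step 5. Effect of redefining the tables.** If Table 35 holds events related to PF-07901801 (with or without PLD) that stop PF-07901801, it covers 4 cells; Table 36, redefined likewise for PLD, covers 4; they share the both/both cell. Coverage is 4 + 4 − 1 = 7 of 9, including both 'related to both, one drug stopped' cells. A row for related to any study drug and any drug stopped covers all 9.

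**The case against.** The protocol sends many unattributable events towards ending all treatment. The synopsis and Section 5.3 list unacceptable toxicity that cannot be attributed to a specific agent as a reason to stop. Events needing more than two dose reductions or a hold over 42 days, and not attributable to one agent, are treated similarly, with an exception for disease control. Table 27 in Section 9.3 removes the participant from study if such an event does not recover after a delay of more than 21 days. Where those events lead to stopping both drugs, they reach Table 37. The monotherapy provision is also worded around PLD as the cause, and an event judged related to PLD only is in Table 36. No passage describes an event related to both drugs that stops PLD alone. This stands as a limit on frequency: a reader might infer from Section 13.3 that the uncounted cell is where unclear events usually go, and the protocol does not support that.

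Nor is related discontinuation a named endpoint. Protocol Section 12.3.1 promises tables of related events and tables of events causing discontinuation, not their cross-classification, and Tables 22–25 and 31–34 deliver those. Appendix 1 allows extra outputs, and in a descriptive study of about 50 participants the cases can be traced individually. This limits the importance. It does not repair Tables 35–37, which are planned and will be read as the related-discontinuation count.

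A reader might also infer that toxicity related to PF-07901801 is understated throughout. It is not. Every such TEAE is in Table 22 or Table 24, and again in Table 25. Only one marginal total is absent, participants with an event related to PF-07901801 with or without PLD; it lies between the larger of the Table 22 and Table 24 counts and their sum.

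**Conclusion.** The gap is real and narrow. As specified in SAP Section 8.4 and Appendix 1, the related-discontinuation summaries omit a TEAE related to both drugs that stops PLD while PF-07901801 continues, including one classed as related to both only through the missing-causality rule. The count is too low whenever such an event occurs, and participant totals are too low when the participant has no other qualifying event. The conclusion rests on reading 'only' and 'both' literally and on the monotherapy provision being used.

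The documents do not support a percentage for the shortfall, a claim that this is the usual fate of unattributable events, or a claim that the reverse case (PF-07901801 alone stopped) is expected. The omission looks unintended: in Section 8.4 the related, grade ≥3, serious and fatal summaries all have an any-study-drug category, and the SAP gives no reason for related discontinuation to differ.

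**What to change.** In SAP Section 8.4 (overall summary and SOC/PT list) and Appendix 1:

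1. Redefine Tables 35 and 36 and their matching rows as TEAEs related to the discontinued drug, alone or together with the other drug, that lead to its permanent discontinuation. State that the event counts whether or not the other drug is also stopped.
2. Keep Table 37 as it is.
3. Add a row for TEAEs related to any study drug that lead to permanent discontinuation of any drug.

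A row for TEAEs related to PF-07901801 with or without PLD in the other related-event tables is an optional addition to presentation, not the correction of an error. It would match the grouping in the DLT definition.

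The cost is table specification and programming only. Causality and action are already collected per drug, and SAP Section 1.1 allows changes before database lock.
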